3.1.1.2. Secondary Endpoints

- Change in percent predicted forced vital capacity (ppFVC) from baseline to Week 52, assessed by spirometry.
- Change in the Grip strength of the hands from baseline to Week 52, assessed by Hand Held Myometry (HHM).
- Change in Left Ventricular Ejection Fraction percentage (LVEF %) from baseline to Week 52, assessed by MRI.
- Change in percent predicted peak expiratory flow (ppPEF) from baseline to Week 52, assessed by spirometry.

3.1.1.3. Safety Assessments

- All treatment emergent adverse events (TEAEs), serious adverse events (SAEs), clinically significant laboratory test abnormalities, discontinuation of treatment due to treatment-related AEs and hypersensitivity/anaphylactic reactions.
- Number and percentage of subjects with hospitalizations due to any serious adverse events with pulmonary and/or cardiac cause(s).
- Number and percentage of subjects with bone fractures

Ulna length measurements for indirect measure of growth velocity (cm/year) for subjects under the age of 18.

3.1.1.4. Exploratory Endpoints

- Change in the subscores of three regional dimensions (High-level (shoulder), Mid-level (elbow), Distal-level (wrist and hand)) of PUL, from baseline to Week 52
- Change in Duchenne Video Assessment severity percentage from baseline to Week 52.

- Change in percent predicted forced expiratory volume at 1 second (FEV1) from baseline to Week 52.
- Analysis of progression of dilated cardiomyopathy (DCM) by genetic analysis.

Fibrosis/MRI assessments:

- Changes in fibrosis score of the biceps brachii, from baseline to Week 52, assessed by MRI.
- Changes in Cardiac fibrosis score from baseline to Week 52, assessed by Late Gadolinium Enhancement (LGE).
- Change in Myocardial Circumferential Strain [Global Circumferential Strain (GCS)] percentage from baseline to Week 52, assessed by cardiac MRI.

3.1.1.5. Pharmacokinetics/pharmacodynamics (PK/PD) assessment

- Population PK/PD analysis.

3.2. Overall Study Design

This is a Phase 3, randomized, double-blind, placebo-controlled multi-center trial to evaluate the efficacy and safety of pamrevlumab in subjects with DMD over a 52-week period.

Approximately 92 subjects will be enrolled in this trial, globally.

Subjects must be fully informed of the potential benefits of approved products and make an informed decision that they prefer to participate in a clinical trial in which they could be randomized to placebo.

Subjects will be randomized in a 1:1 ratio to one of the two study treatment arms; pamrevlumab or placebo.

This trial has three study periods:

- Screening period: Up to 4 weeks
- Treatment period: 52 weeks
- Safety Follow-up period/final assessment: A visit 28 days (+/- 3 Days) and a final safety follow-up phone call 60 days (+ 3 Days) after the last dose.

In the screening period, subjects will be evaluated per the protocol inclusion/exclusion criteria to determine eligibility for participation in this trial.

During the treatment period, each subject will receive pamrevlumab or placebo at 35 mg/kg every 2 weeks for up to 52 weeks.

Subjects who complete the study may be eligible for an open-label extension (OLE), offering extended treatment with pamrevlumab.

Subjects who discontinue study treatment for any reason should be encouraged to return to the investigative site to complete final safety and efficacy assessments.

A schematic overview of the study is provided in [Figure 1](#). A detailed overview of assessments and the timing of assessments is provided in [Appendix 1](#).

[figure not shown]
3.2.1. Study Duration

All subjects are encouraged to complete up to 27 doses of study treatment, an End of Study (EOS)/Safety follow-up visit 28 days (+/- 3 Days) and a final safety follow-up phone call 60 days (+ 3 Days) after the last dose. Subjects who discontinue the study early, for any reason, will need to come in for an early termination visit (ET) 28 days (+/- 3 Days) after the last dose and a final safety follow-up phone call 60 days (+ 3 Days) after the last infusion. If a subject withdraws from the study after randomization and prior to dosing, an ET visit and safety follow-up phone call are not required. See also [Section 4.3](#) for mandatory discontinuation reasons, and [Section 4.4](#) for procedures related to the ET.

Subjects who complete the study may be eligible for rollover into an open-label, extension study which will provide data on the long term safety and efficacy of pamrevlumab.

End of trial is defined as the date at which the last subject completes the final safety follow-up phone call.

Figure 1: FGCL-3019-093 Study Schema

Abbreviations: EOS= End of Study, ET=Early Termination

Subjects who discontinue the study early, for any reason, will complete an early termination visit 28 days (+/- 3 Days) and a final safety follow-up phone call 60 days (+ 3 days) after the last infusion.

3.2.2. Placebo Control Group

In order to evaluate the effect of treatment with pamrevlumab on the endpoints described in [Section 3.1.1](#) approximately 50% of subjects will be randomized to placebo treatment.

For DMD subjects, one of the only current FDA approved treatment options is systemic corticosteroids, which is available to them as part of this protocol. Therefore, placebo control, given with systemic corticosteroids, is appropriate and ethical. Additionally, all study subjects, including those randomized to placebo and who complete the study may be offered crossover to the active arm in the OLE.

3.3. Subject ID Assignment

Subjects that sign consent will be assigned an 8 digit Subject ID number consisting of a four digit site number and a 4 digits Subject ID starting with 1xxx. Subject numbering will be assigned sequentially as subjects are recruited/screened (e.g., 1001, 1002, and 1003, etc.).

3.4. Randomization and Treatment Assignment

3.4.1. Randomization

Approximately 92 subjects will be randomized 1:1 to receive either pamrevlumab or placebo, resulting in approximately 46 subjects in treatment arm A and 46 subjects in treatment arm B.

Randomization schedules will be prospectively prepared. Automated randomization and treatment assignments will be performed by an Interactive Response System (IXRS or IRT).

3.4.2. Treatment Assignment

Subjects will be randomized 1:1 to one of two treatment arms:

Arm A	Arm B
pamrevlumab 35 mg/kg IV Q2 weeks + systemic deflazacort or equivalent potency of corticosteroids administered orally	matching placebo IV Q2 weeks + systemic deflazacort or equivalent potency of corticosteroids administered orally

3.5. Blinding

This is a double-blind, placebo-controlled study. The Investigator, study site staff, subjects, selected sponsor clinical team and designees are blinded to study drug assignment. Blinded treatment with a placebo control is the gold standard method for obtaining unbiased assessments of safety and efficacy in clinical trials of investigational drugs such as pamrevlumab.

3.5.1. Maintenance of Blinding

The study blind will be maintained for all parties specified above throughout the study. Pamrevlumab and placebo will be identical in appearance, packaging, and labeling in order to maintain the study blind. The blind will remain intact even while subjects rollover into the open label extension and until the database is locked for the main study.

3.5.2. Request for Unblinding of Treatment Assignment

Investigators, study site staff and subjects will remain blinded to treatment assignments until study completion and database lock.

Breaking the blind during the study (for a single subject) should be considered only when knowledge of the treatment assignment is deemed essential by the Investigator due to immediate safety concerns, or is considered essential for the immediate subject management. FibroGen approval is not a prerequisite for the investigator to unblind a subject. It is the responsibility of the investigator to promptly document and notify the Sponsor of any unblinding.

The IRT system allows authorized users to break the blind for a specific subject. Detailed instructions for unblinding are provided in the IRT user manual.

4. SELECTION AND WITHDRAWAL OF SUBJECTS

4.1. Subject Inclusion Criteria

In order to be eligible for inclusion in this trial, a subject must meet all of the following:

Age, Consent, and Contraception

1. Males at least 12 years of age, non-ambulatory at screening initiation
2. Written consent by patient and/or legal guardian as per regional/ country and/or IRB/IEC requirements
3. Male subjects with partners of childbearing potential must use contraception during the conduct of the study, and for 12 weeks after the last dose of study drug.

DMD Diagnosis:

4. Medical history includes diagnosis of DMD and confirmed Duchenne mutation using a validated genetic test

Performance criteria:

5. Brooke Score for Arms and Shoulders ≤ 5
6. Able to undergo MRI test for the upper arm extremities (Biceps Brachii muscle) and cardiac muscle
7. Able to perform spirometry

Pulmonary and Cardiac criteria:

8. Average (of Screening and Day 0) percent predicted FVC between 45 and 85, inclusive
9. Left ventricular ejection fraction $\geq 50\%$ as determined by local cardiac MRI read at screening or within 3 months prior to randomization (Day 0)
10. If subjects have a history of cardiomyopathy, then subject must be on a stable dose of cardiomyopathy/ heart failure medications (e.g., angiotensin converting enzyme inhibitors, aldosterone receptors blockers, angiotensin- receptor blockers, and beta-blockers) for at least 1 month prior to screening. If subjects have no diagnosis of cardiomyopathy, then no dose of cardiomyopathy/heart failure medication is required for eligibility.
11. On a stable dose of systemic corticosteroids for a minimum of 6 months, with no substantial change in dosage for a minimum of 3 months (except for adjustments for changes in body weight) prior to screening. Corticosteroid dosage should be in compliance with the DMD Care Considerations Working Group recommendations (e.g. prednisone or prednisolone 0.75 mg/kg per day or deflazacort 0.9 mg/kg per day) or stable dose. A reasonable expectation is that dosage and dosing regimen would not change significantly for the duration of the study.

Vaccination:

12. Agreement to receive annual influenza vaccinations during the course of the study.

Laboratory criteria:

13. Adequate renal function: cystatin C ≤ 1.4 mg/L
14. Adequate hematology and electrolytes parameters:
 - a. Platelets $>100,000$ /mcL
 - b. Hemoglobin >12 g/dL
 - c. Absolute neutrophil count >1500 / μ L
 - d. Serum calcium (Ca), potassium (K), sodium (Na), magnesium (Mg) and phosphorus (P) levels are within a clinically accepted range for DMD patients.
15. Adequate hepatic function:
 - a. No history or evidence of liver disease
 - b. Gamma glutamyl transferase (GGT) ≤ 3 x upper limit of
 - c. Total bilirubin ≤ 1.5 xULN

4.2. Subject Exclusion Criteria

Subjects will be ineligible for and excluded from this trial if any of the following apply:

General criteria:

1. Previous exposure to pamrevlumab
2. BMI ≥ 40 kg/m² or weight >117 kg
3. History of:
 - a. allergic or anaphylactic reaction to human, humanized, chimeric or murine monoclonal antibodies
 - b. hypersensitivity to study drug or any component of study drug
 - c. hypersensitivity reaction to Gadolinium-based Contrast Agents (GBCA) required for MRI acquisition
4. Exposure to any investigational drug (for DMD or not), in the 30 days prior to screening initiation or use of approved DMD therapies (e.g., eteplirsen (exondys 51), ataluren, golodirsen (vyondys 53), casimersen (amondys 45)) within 5 half-lives of screening, whichever is longer, with the exception of the systemic corticosteroids, including deflazacort

Cardiac, Renal, and Pulmonary assessment:

5. Severe uncontrolled heart failure (NYHA Classes III-IV), or renal dysfunction, including any of the following:
 - a. Need for intravenous diuretics or inotropic support within 8 weeks prior to screening
 - b. Hospitalization for a heart failure exacerbation or arrhythmia within 8 weeks prior to screening
 - c. Patients with glomerular filtration rate (GFR) of less than 30 mL/min/1.73m² or with other evidence of acute kidney injury as determined by investigator
6. Arrhythmia requiring anti-arrhythmic therapy
7. Requires ≥ 16 hours continuous ventilation

8. Hospitalization due to respiratory failure within the 8 weeks prior to screening
9. Poorly controlled asthma or underlying lung disease such as bronchitis, bronchiectasis, emphysema, recurrent pneumonia that in the opinion of the investigator might impact respiratory function

Clinical judgments:

10. The Investigator judges that the subject will be unable to fully participate in the study and complete it for any reason, including inability to comply with study procedures and treatment, or any other relevant medical or psychiatric conditions which could confound efficacy assessment and/or safety assessment.

4.3. Subject Withdrawal Criteria

Subjects may withdraw from the study at any time, for any reason. If a subject or investigator determines subject should discontinue from treatment, the subject has the option to remain on study. If the subject remains on study, they should continue to perform on-study assessments until the end of study visit or subject terminates for one of the below reasons.

Mandatory reasons for withdrawing the subject from the study include the following:

- Any safety concern in the Investigator's opinion, that precludes further study participation
 - Pamrevlumab will be permanently discontinued in case of serious or life-threatening allergic reactions
- Major protocol deviation to inclusion/exclusion that substantially affects subject safety
- Withdrawal of Consent (reason of withdrawal should be obtained)

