4.4. Subject Withdrawal Procedure

Subjects who discontinue the study early will complete an Early Termination visit 28 days (+/- 3 days) and complete a final safety follow-up phone call 60 days (+3 Days) after the last infusion. If a subject is randomized but not dosed with IP before Early Termination on Day 0, an Early Termination visit is not required.

Note: At the Early Termination visit, PFTs and MFTs must be conducted. MRIs do not have to be repeated if the last one was performed within 4 weeks of this visit.

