**Table 9: Analysis Visit Window for Muscle Function Tests (MFT)**

Analysis Visit	Target Day	Start Day	End Day
Baseline	Last value before the first study drug infusion (or randomization date if no infusion received)		
Week 16	113	2	155
Week 28	197	156	239
Week 40	281	240	323
Week 52	365	324	**

\*\* before the first study drug infusion in the OLE period or end of randomization treatment period

Note: All assessments beyond 60 days post last infusion will be excluded from summary tables for labs.

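### Protocol 4.3 makes a safety-relevant eligibility deviation end study participation and files a drug-stopping rule under the same heading, so some post-treatment PUL scores that the treatment-policy analysis wants may not be collected (minor)

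*Protocol*

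**What the plan says.** **Withdrawal rules.** Protocol 4.3 first says that when treatment is to stop, "the subject has the option to remain on study". Such a subject should go on with assessments until the end-of-study visit or until he terminates for a reason listed below. The list is introduced by "Mandatory reasons for withdrawing the subject from the study include the following" and has three main bullets:

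- a safety concern that in the investigator's opinion rules out further participation; its sub-bullet, which speaks of the drug only, reads "Pamrevlumab will be permanently discontinued in case of serious or life-threatening allergic reactions" and stands one level below;
- an eligibility problem, given in the list as "Major protocol deviation to inclusion/exclusion that substantially affects subject safety" without further detail;
- consent being withdrawn.

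Protocol 3.2.1 points to this section "for mandatory discontinuation reasons". SAP 6.2 counts as a possible important deviation a subject who met withdrawal criteria and was not withdrawn.

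**What is measured after withdrawal.** Under Protocol 3.2.1, a subject who leaves the study early "will need to come in for an early termination visit (ET) 28 days" (plus or minus 3) after the last dose. Protocol 4.4 adds: "At the Early Termination visit, PFTs and MFTs must be conducted". The muscle function tests include PUL. No later efficacy visit is scheduled.

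**What the analysis wants.** SAP 6.6.1.1.1 adopts a treatment-policy strategy. SAP 6.6.1.1.4 includes PUL after treatment discontinuation up to Week 52. SAP 6.6.1.1.3 handles missing values after discontinuation implicitly under missing at random (MAR).

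**Open-label extension (OLE).** Protocol Appendix 3 opens by admitting subjects who reach Week 52 whatever number of infusions they received, and SAP 3.5 agrees. The Study Enrollment paragraph of the same appendix requires completed treatment through the primary endpoint.

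**The concern.** A treatment-policy estimate needs outcomes measured after the drug is stopped. An eligibility deviation that makes infusions unsafe calls for stopping infusions. It does not usually make a PUL test unsafe, yet 4.3 ends participation. The allergic-reaction rule concerns the drug alone, but its place in the list and the cross-reference in 3.2.1 invite a site to treat it as an exit rule. SAP 6.2 adds pressure in the same direction, because keeping such a subject could be recorded as a deviation.

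If an active-arm subject leaves this way, MAR projects his on-drug course to Week 52. Where benefit stops with the drug, that inflates the estimated difference. A placebo subject lost in the same way adds no such inflation, and there is none if the drug has no effect. Jump-to-control and tipping-point analyses (SAP 6.6.1.2.4 and 6.6.1.2.5) probe the assumption but cannot recover the scores.

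**Working it through.** **1. The plan's own figures.** With difference 2.0, SD 2.9 and two-sided alpha 0.05, the exact t-test needs 46 per arm, or 92 in total (power 90.5%). With 41 per arm, power is 87.0%. Both match the plan (about 92 in Protocol 8.1; 87% with 82 mITT subjects in SAP 7). I assume 41 active subjects, from 82 at 1:1.

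**2. Timing of the last PUL.** Nominal dose day = 7 x week + 1. The Early Termination (ET) visit is 28 +/- 3 days later. The Week 52 window for muscle function tests opens on Day 324 (SAP Appendix 2, Table 9).

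| Last dose | Dose day | ET days | Visit window |
|---|---|---|---|
| Week 40 | 281 | 306-312 | Week 40 |
| Week 42 | 295 | 320-326 | borderline |
| Week 44 | 309 | 334-340 | Week 52 |

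Of the 27 infusion slots, the 21 from Day 0 to Week 40 give no Week 52-window score if they are the last dose, and one is borderline. This window matters for the visit-based analyses only. The primary random coefficient model (SAP 6.6.1.1.5) uses elapsed weeks and all valid values, so the ET score enters at its actual time.

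**3. Inflation per lost active subject, before the model.** Assume that 2.0 points accrue linearly over 52 weeks and that accrual stops at last dose w. The inflation is 2.0 x (52 - w)/52/41:

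- w = 10: 0.039
- w = 28: 0.023
- w = 40: 0.011

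If half the later benefit persists, these become 0.020, 0.011 and 0.006. If all benefit is lost, the figure is 2.0/41 = 0.049.

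**4. In the model.** This is the expected generalized least squares estimate at Week 52 minus the treatment-policy truth. Visits are at Weeks 16, 28, 40 and 52, and the Week 52 SD is 2.9. Assumed: residual SD 1.0-2.0, and a random slope with or without a random intercept (SD 0-1), because the protocol text has both effects and the SAP sample code has the slope only. A withdrawn subject keeps his earlier scores and an ET score at week w + 4.

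| Last dose | Withdrawn, ET score kept | All visits collected | Net gain from collecting |
|---|---|---|---|
| Week 10 | 0.035-0.039 | 0.000 | 0.035-0.039 |
| Week 28 | 0.020-0.021 | 0.002 | 0.017-0.018 |
| Week 40 | 0.009 | 0.003 | about 0.006 |

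Some inflation remains with full collection because a straight line does not fit a mid-study stop.

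**5. Scale.** SE = 2.9 x sqrt(2/41) = 0.64. The net gain per subject is 0.006/0.64 = 1% to 0.039/0.64 = 6% of one SE. A quarter of one SE is 0.16 points. The number of active subjects needed to reach it is:

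- Week 10: 0.16/0.039 = 4.1, about 4
- Week 28: 0.16/0.0175 = 9.1, about 9
- Week 40: 0.16/0.006 = 26.7, about 27 (from the rounded gain)

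**6. Power.** If 1 to 5 of the 82 contributed nothing at all, t-test power would fall from 87.0% to about 86.6% for one and 84.6-84.8% for five. This bounds the loss from above, since these subjects do contribute.

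**The case against.** The main defence is that the plan already handles most of this, and that stands. Protocol 4.3 lets a subject off drug stay and be assessed. Protocol 3.2 and SAP 3.5 say that subjects who stop treatment for any reason should be encouraged to return for final assessments. Removing someone whose ineligibility endangers him is also a defensible safety choice. The point therefore covers only the two listed items.

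Four stronger readings are tempting and are not supported:

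- **That a serious allergic reaction forces study exit.** The sub-bullet stops pamrevlumab only, and its parent bullet applies only when the concern rules out further participation. The fault is ambiguous placement.
- **That a withdrawn subject drops out of the primary analysis, or that Day 324 decides whether his ET score counts there.** The primary model uses continuous time and keeps that score. The window governs visit-based analyses such as the MMRM and multiple imputation.
- **That about 7 losses at Week 28, or 14 at Week 40, reach a quarter of one SE.** Those counts follow from the pre-model figures in step 3. They overstate what the fix recovers. On the net gain the counts are about 9 and 27.
- **That Protocol 6.1.2 requires completed treatment for the OLE.** It says those who complete 52 weeks of treatment may be eligible, and it bars only those who leave the main study early. The contradiction lies within Appendix 3. It concerns access to the OLE, not PUL collection, and subjects with an allergic reaction to study drug are excluded from the OLE in any case.

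**Conclusion.** The concern holds as a minor one. Followed as written, 4.3 ends follow-up for one group whose PUL the estimand asks for, and it invites the same for another. For such a subject with a last dose at Week 40 or earlier, nothing near Week 52 is observed and MAR fills the gap.

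The size rests on three assumptions: the 2.0-point benefit accrues linearly, it stops with the drug, and there are 41 active mITT subjects. The documents give no rate for serious allergic reactions, eligibility deviations or discontinuation, so the total effect cannot be stated. At 1-6% of one SE per active subject lost, it would take an unusual number of such exits to matter. This is a cheap improvement and not a threat to the trial's conclusion.

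**What to change.** In Protocol 4.3:

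- make serious allergic reactions and safety-relevant eligibility deviations reasons to stop study drug;
- keep as study-ending reasons only withdrawal of consent and a safety concern that rules out further participation;
- state that subjects off drug keep the scheduled PUL, grip, pulmonary function and MRI visits through Week 52, leaving out any assessment that is unsafe for that subject (for example contrast MRI with gadolinium hypersensitivity or GFR below 30, as in exclusions 3c and 5c).

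No drug-stopping rule is loosened.

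Separately, align the Study Enrollment sentence of Appendix 3 with the opening of that appendix and SAP 3.5, and keep the exclusion for allergic reactions. Protocol 6.1.2 needs at most a clarification.

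The cost is amendment text or a clarification letter to sites, since the visits are already scheduled. The downside is some visits without infusions. Only subjects still in the main study benefit, and missed visits cannot be recovered.
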